1.2 Relevance

Transfusion practice has already been studied before on the ICU and the operating theater^{17,19–21}. However, these studies were held in a limited number of hospitals within the same country, were limited to only one type of transfusion, are often outdated and difficult generalizable to other hospitals and regions. Since these large observational studies, numerous of randomized controlled trials on RBC transfusion have been published supporting the safety of more restrictive transfusion strategy^{7–10}. However, current

InPUT-study Protocol, dated 09-09-2020

transfusion practice remains unknown. There is a need 1) to describe current transfusion practice for RBC but also for other blood components and coagulation factors, 2) to identify area of improvement, 3) to have large observational data to generate hypotheses on optimal transfusion triggers in subgroups of critically ill patients including patients with brain injury, cardiovascular diseases and elderly patients.

This study will be the first worldwide transfusion practice point prevalence trial on the ICU, which studies the practice of administration of different blood products and coagulation factors.

OBJECTIVES

Primary Objective:

- Number of red blood cell, platelet, and coagulation factors in correlation to haemoglobin levels, platelet count and INR (or PT) respectively.

Secondary Objectives:

- To evaluate which other triggers such as hemodynamic or comorbidities influence RBC transfusion practice.
- To compare haemoglobin levels in transfused patients with nadir levels of haemoglobin in non-transfused patients
- To compare platelet count in transfused patients with platelet to nadir platelet count in non-transfused patients
- To compare INR (or PT) in transfused patients with plasma to nadir level of INR(PT) in non-transfused patients
- To compare transfusion practice between different subgroups of patients including shock septic, haematology, cardiovascular disease without acute coronary diseases and coronary disease
- Association between restrictive and liberal RBC transfusion strategy on ICU length of stay and 28-day mortality
- Association between restrictive and liberal platelet transfusion strategy on ICU length of stay and 28-day mortality
- Association between restrictive and liberal coagulation factor suppletion strategy on ICU length of stay and 28-day mortality

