2. STUDY DESIGN

This study is a prospective, descriptive study and only includes objective data collected as part of routine care. No intervention takes place. ICUs in different world regions will be asked to participate in this study. Each centre can choose a week to participate from several pre-specified weeks. All newly admitted patients on the ICU in that specific week will be included and followed until discharge and/or 28 days (see Figure 1 for study flow).

A transfusion event is defined as the administration of a blood derived product or coagulation factor with as aim to treat or prevent anaemia, bleeding and/or coagulopathy. This includes administration of red cell concentrates, platelet concentrates, plasma and coagulation factors including fibrinogen concentrate, cryoprecipitate and prothrombin complex. For each transfusion event data will be collected prospectively using a questionnaire on prescription behaviour. Also transfusions administered on the operating theatre while admitted to the ICU will be included for analysis.

The daily questionnaire contains clinical an laboratory data. These data include nadir haemoglobin levels, platelet count and INR or PT. This data will be necessary to compare data between patients who did receive a transfusion to patients who did not receive transfusions. Furthermore, information about 24h fluid balance and anticoagulants administration will be collected. Finally after 28 days patient outcome data: length of ICU stay and 28-day mortality will be collected.

STUDY POPULATION

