3.1.2 Secondary study parameters/endpoints

Secondary parameters will be:

- Mortality and length of stay in the ICU.
- Differences of transfusion regimes between world regions
- Differences of transfusion practices between different patient subgroups

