3.2 Data collection

All newly admitted patients at the ICU older than 18 years will be included for seven consecutive days. At the start, baseline characteristics will be scored prospectively. Also, patients will be scored daily using daily questionnaires until discharge with a maximum of 28 days. At the day 28, patient outcomes are scored irrespective whether they were discharged. Furthermore, for each transfusion event or administration of coagulations factors a questionnaire will be filled in. See Figure 1 for the workflow.

Figure 1. Workflow InPUT study

The following data will be collected:

Baseline characteristics:

- Demographics
- SOFA score at inclusion
- Type of admission
- Presence or absence and the type of shock on the study day
- Heart rate, systolic and diastolic blood pressure
- Ventilator settings
- Renal replacement therapy during that day

Questionnaire per transfusion event:

- General
 - \circ Active bleeding
 - Bleeding control
 - Red cell transfusion
 - Haemoglobin(Hb)/haematocrit (Ht) level
 - Hb threshold for this patient
 - Presence of physiological trigger, and which trigger has been used.
 - Transfusion relevant comorbidity

- Number of units transfused
- Origin of transfusion product (e.g. allogeneic, autologous, cell salvaged blood)
- Platelet transfusion
 - Platelet count prior to transfusion
 - Platelet count threshold for transfusion for this patient
 - Type of Platelet concentrate
 - Anticoagulant usage the past 72 hours
 - Usage of point of care to assess blood coagulation: ROTEM or multiplate
 - Number of units transfused
 - Upcoming procedures
- Plasma
 - INR prior to transfusion
 - $_{\odot}$ Anticoagulant usage the past 72 hours
 - Usage of point of care to assess blood coagulation
 - Amount of plasma transfused
 - Upcoming procedures
- Prothrombin complex concentrate (i.e. Cofact ®).
 - o INR or PT
 - Dosage of prothrombin complex concentrate
 - Usage of point of care to assess blood coagulation
 - Upcoming procedures
- Massive transfusion protocol:
 - Lowest haemoglobin level
 - Lowest platelet count
 - o INR
 - Usage of point of care to assess blood coagulation
 - Number of Red blood cell units transfused
 - Number of platelet concentrate units transfused
 - Amount of plasma transfused
 - Tranexamic acid, fibrinogen, rFactor VIIa, Cryoprecipitate, factor XIII, apropitin, novoseven (=eptacog alfa)
 - Bleeding control

Daily questionnaire

- Estimated blood loss
- Total number of transfused RBCs

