5.2 Secondary study parameter(s)

Data obtained during this study will be checked for distribution. Normal data will be analysed using ANOVA analysis or student t-test. Non-parametric data will be analysed with Mann Whitney U-test or Kruskall wallis. Categorical data will be compared using chisquare or Fisher's exact test. A logistic regression model will be performed to assess independent association between number of transfusions and outcome (mortality and ICU length of stay). Results of the logistic regression will be reported as adjusted odds ratio (OR) with 95% confidence intervals.

If a sufficient number of patients can be included, propensity score matching for a liberal and a restrictive transfusion regime will be performed for each type of product. The criteria for a liberal an restrictive transfusion regime for red blood cells, platelets and plasma will be determined during the study. A p-value <0.05 will be considered to be significant.

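### Section 5.2 assigns ICU length of stay, a duration, to a logistic regression with odds ratios, without defining a binary or ordinal outcome or a rule for deaths in the ICU

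*Protocol*

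**What the plan says.** The adjusted analysis of patient outcomes is set out in Protocol section 5.2: "A logistic regression model will be performed to assess independent association between number of transfusions and outcome (mortality and ICU length of stay"). The next sentence fixes the effect measure: "Results of the logistic regression will be reported as adjusted odds ratio (OR) with 95% confidence intervals". Read across the two sentences, the text runs "outcome (mortality and ICU length of stay). Results of the logistic regression will be reported as adjusted odds ratio (OR"), so the odds ratio is meant for both outcomes. The significance rule covers the whole section: "A p-value <0.05 will be considered to be significant".

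Length of stay is recorded as a duration. Section 2 (Study design) states: "Finally after 28 days patient outcome data: length of ICU stay and 28-day mortality will be collected". Section 3.1.2 lists it beside mortality as one secondary parameter, "Mortality and length of stay in the ICU", and the day-28 list in section 3.2 has it as an item of its own. On follow-up, section 3.2 says that "patients will be scored daily using daily questionnaires until discharge with a maximum of 28 days".

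The secondary objectives also name length of stay, for example "Association between restrictive and liberal RBC transfusion strategy on ICU length of stay and 28-day mortality", with parallel objectives for platelets and coagulation factors. Section 5.2 provides propensity score matching for liberal against restrictive regimes if numbers allow.

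Nowhere does the protocol define a prolonged stay, group the stay into ordered categories, or say how a stay that ends in death is to be scored.

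**The concern.** A binary logistic model needs a yes/no outcome, and a number of days is not one. The protocol has gone beyond leaving detail open: it names the model and the effect measure, and these do not fit one of the two outcomes it names.

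Two things are at stake. First, an odds ratio for length of stay exists only after someone chooses a cut-off or a grouping. With none in the protocol, the choice can be made with the data in view, and the result moves with it. Second, an ICU stay ends in one of two opposite ways, discharge alive or death. If the stay is taken as recorded, a patient who dies on day 1 has a very short stay. Should transfused patients die more often or earlier than the others, their stays could look favourable for that reason alone.

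**Working it through.** The protocol gives no effect size, variance, mortality or discharge rate for this outcome, so it has no figure of its own to reproduce. All hazards below are assumptions chosen for illustration.

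**1. Can the model be run as written?** No. Fitting a binary logit to stays in whole days stops with an error, because the outcome must lie between 0 and 1.

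**2. Dependence on the cut-off.** Assume constant daily discharge hazards of 0.20 and 0.14 and no deaths. Then P(stay > c) = exp(−hazard × c), and OR = odds(0.14 group) / odds(0.20 group).

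| Cut-off c (days) | P, 0.20 group | P, 0.14 group | OR |
|---|---|---|---|
| 3 | 0.549 | 0.657 | 1.58 |
| 7 | 0.247 | 0.375 | 1.84 |
| 14 | 0.061 | 0.141 | 2.53 |

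The hazard ratio for discharge is 0.14/0.20 = 0.70 throughout. The odds ratio runs from 1.58 to 2.53 on the cut-off alone.

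**3. Effect of how deaths are scored.** Assume the same discharge hazard, 0.20 per day, in both groups, and death hazards d of 0.02 (group A) and 0.04 (group B). Deaths in the ICU by day 28 are d/(0.20 + d) × [1 − exp(−28(0.20 + d))], which is 9.1% in A and 16.6% in B.

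Cut at 7 days, death merely ends the stay: P(stay > 7) = exp(−7(0.20 + d)).
- A: exp(−1.54) = 0.2144, odds 0.2729
- B: exp(−1.68) = 0.1864, odds 0.2291
- OR (B/A) = 0.2291/0.2729 = 0.84

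Cut at 7 days, death is an unfavourable outcome: P(not discharged alive by day 7) = 1 − [0.20/(0.20 + d)] × [1 − exp(−7(0.20 + d))].
- A: 1 − 0.9091 × 0.7856 = 0.2858, odds 0.4002
- B: 1 − 0.8333 × 0.8136 = 0.3220, odds 0.4749
- OR (B/A) = 0.4749/0.4002 = 1.19

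A simulation of 400,000 patients under the same hazards gives 0.85 and 1.19.

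The same formulas at other cut-offs, and with a larger difference in death hazard, give:

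| Death hazard, A vs B | Cut-off (days) | OR, death ends stay | OR, death worst |
|---|---|---|---|
| 0.02 vs 0.04 | 3 | 0.89 | 1.05 |
| 0.02 vs 0.04 | 7 | 0.84 | 1.19 |
| 0.02 vs 0.04 | 14 | 0.75 | 1.59 |
| 0.02 vs 0.08 | 7 | 0.60 | 1.57 |
| 0.02 vs 0.02 | any | 1.00 | 1.00 |

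In each scenario with unequal death hazards, the group with the higher hazard looks better on recorded stay and worse once death counts against it. With equal death hazards there is no distortion.

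**4. What the proposed analysis would show.** In the 0.02 versus 0.04 scenario the cause-specific hazard ratio for discharge alive is 0.20/0.20 = 1. The cumulative incidence of discharge alive by day 7 is 1 − 0.2858 = 71.4% in A and 1 − 0.3220 = 67.8% in B. Reported together, these show that the groups differ in deaths and not in the rate of discharge.

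**The case against.** The strongest defence is that an odds ratio for length of stay can be legitimate. An outcome such as discharged alive by a given day is binary, puts deaths on the unfavourable side and suits logistic regression. A proportional-odds model with death as the worst category would also give an odds ratio. A cut-off and a rule for deaths are commonly left to a statistical analysis plan, and one may exist that is not shown. The study is descriptive, and its primary endpoint uses descriptive statistics only.

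This limits the point without removing it. The protocol defines none of these outcomes, yet it does fix the model and the effect measure. The mismatch is therefore in the text itself. Several stronger readings are tempting and should not be drawn:

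- **That the plan says early deaths count as short stays, or that every split must do so.** It says nothing on the matter. The misclassification is the default result of using the recorded stay, and a suitably defined binary outcome avoids it.
- **That patients still in the ICU at day 28 are misplaced.** A split at any cut-off below 28 days classes them correctly as long stays, and a rank test puts them correctly at the top. Section 5.2 also lists its tests by type of data and does not assign one to length of stay.
- **That the three objectives on restrictive against liberal strategy rest on this model.** Its exposure is the number of transfusions. The strategy comparison is covered by the conditional propensity matching. The handling of deaths matters there too, but the logistic sentence does not govern it.
- **That a fixed share of information is lost.** An efficiency figure for dichotomising would need an assumed distribution and an assumed cut-off, and the protocol gives neither.

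**Conclusion.** The point holds. Section 5.2 names a model and an effect measure that cannot be applied to ICU length of stay as the protocol collects it. That conclusion rests on the text alone.

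The second part, on deaths, is conditional. It applies if the recorded stay is used without a rule for deaths, and it distorts the comparison only when death rates differ between the groups. The odds ratios of about 0.84 and 1.19 at 7 days show that the sign can change under plausible-looking but assumed hazards. They do not estimate the bias in this study, and the protocol offers no inputs from which to estimate it.

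This should be fixed before analysis. It affects a secondary outcome in an observational study and leaves the descriptive primary endpoint untouched.

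**What to change.** Reword section 5.2 as follows:

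- Restrict the logistic regression and its adjusted odds ratios to 28-day mortality.
- Analyse ICU stay as time to ICU discharge alive, with death in the ICU as a competing event and administrative censoring at day 28. Report hazard ratios with 95% confidence intervals, stating whether they are cause-specific or subdistribution, together with the cumulative incidence of discharge alive.
- An acceptable alternative is ICU-free days to day 28 with deaths scored as the worst value. If an odds ratio is preferred, define the binary or ordinal outcome and its rule for deaths before the data are seen.
- Apply the same handling of deaths to length of stay in the propensity-matched comparisons.

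The cost is a few sentences and slightly more analysis work. One check is needed on the data. The day-28 list in section 3.2 names 28-day mortality and ICU length of stay, but 28-day mortality includes deaths after ICU discharge and does not by itself show how the ICU stay ended. The sponsor should confirm that the case report form records whether the stay ended in death. If it does not, one item has to be added or retrieved.

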6. ETHICAL CONSIDERATIONS

6.1 Regulation statement

This trial will be conducted according to the principles of the Declaration of Helsinki as stated in the current version of Fortaleza, Brazil, 2013 and in accordance with the Medical Research Involving Human Subjects Act (WMO).

6.2 Recruitment and consent

Since the proposed study is an observational study, no research related interventions will take place. Therefore, no ethical concerns exist. Institutional review board approval will be obtained by the participating institutions according to local ethical regulations. If a waiver is not granted informed consent forms and written patient information will be provided by the sponsor.

6.3 Benefits and risks assessment, group relatedness

This study is a descriptive study and only includes objective data collected as part of routine care. No intervention takes place. Therefore, this study does not result in any risk or burdens to patients

6.4 Compensation for injury

The sponsor/investigator has a liability insurance which is in accordance with article 7 of the WMO. However, as this study is an observational study, an exception from the requirement for insurance to cover for damage to research subjects through injury or death caused by the study is applicable.

7. ADMINISTRATIVE ASPECTS, MONITORING AND PUBLICATION

7.1 Handling and storage of data and documents

Subject data will be stored anonymously using a coding system. The codebook will be stored digitally and in paper. The paper version will be stored behind a lock and the digital form will be encrypted with a double password. All data will be stored for the length of the study and for 15 years afterwards. All handling of personal date will comply with the European General Data Protection Regulation act.

7.2 Quality Assurance

The sponsor is responsible for implementing and maintaining quality assurance and quality control systems with written standard operating procedures to ensure that trials are conducted and data are generated, documented and reported in compliance with the protocol and regulatory requirements.

Quality control should be applied to each stage of data handling to ensure that all data are reliable and have been processed correctly.

Not

7.3 Public disclosure and publication policy

We are free to make a publication and have no restrictions made by a sponsor.

8. TIMELINE

April 2018: January-February 2019:	Writing study protocol Pilot study in Amsterdam testing feasibility
April 2018-December 2019:	Recruiting Centers
August 2019-May 2020:	Obtaining approval from institutional review boards for each country
March 2020	Start data collection
February 2021	Data analysis
March 2021	Writing manuscript

